## **Study Design**

This study is divided into 2 parts (studies), whereby the first part will be 2X2 comparing NJOY 5% and 3% to test the effects of partial nicotine reduction, and the second part will be using the NIDA Standardized Research Electronic Cigarette (SREC) for Clinical Research 5% and 0% (placebo), to test the effect of the total reduction using the same pods and juices from the same manufacturer.

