## Assessing the effect of nicotine reduction on ENDS users' addiction and exposure

### Background

The use of electronic nicotine delivery systems (ENDS) has reached epidemic levels among young people in the US. While estimates vary, ENDS have become the leading tobacco product used by young people in this country. ENDS heat and vaporize a nicotine-containing liquid to produce an inhalable aerosol mist. In addition to dependence-producing nicotine, ENDS emit other toxicants including aldehydes/carbonyls, a class of potent respiratory toxicants implicated in most non-cancer pulmonary diseases in cigarette smokers. Evidence indicates that young people using ENDS are likely to accelerate use, become nicotine dependent (ND), and initiate cigarette smoking. Epidemiological studies and market analysis moreover, suggests that "pod-mod" ENDS, JUUL in particular, had the biggest impact on the ENDS epidemic among young people. Unlike older ENDS generations, JUUL pioneered the use of nicotine salts which allowed to deliver high doses of nicotine in a smooth (protonated) form to users. Thus, addressing the addictiveness of ENDS through nicotine reduction (NR) can be a major regulatory strategy to reduce ENDS use among young people. In cigarette smokers, several observational studies and clinical trials have shown that smokers who switch to low nicotine cigarettes reduce daily nicotine intake, smoke fewer cigarettes, report lower dependence, and show higher trends in quitting. Similar patterns are expected in ENDS users, as our preliminary study of NR in young JUUL users shows that it leads to decreased satisfaction, dependence suppression, and intention to use in the future. However, reducing ENDS nicotine levels carries the risk of compensatory puffing and increased exposure. Evidence suggests that such compensation is dose and ND related, where very low nicotine products and beginning users are likely to have minimal compensation. Accordingly, assessing the potential role of NR regulations to reduce ENDS use and addiction requires standardized comparisons involving a range of NR levels and ENDS users at different stages of their use trajectory. It also requires assessing a wide array of outcomes to evaluate the effects of compensatory puffing on exposure to key pulmonary toxicants. These goals can be achieved by applying within-between subject comparisons to assess responses to a range of NR levels (partial vs. total) in ENDS users with different use profiles. Our team has pioneered the use of clinical and analytical lab methods to provide rapid and robust evidence about promising tobacco product manipulations for regulatory purposes (e.g. flavor). We plan to use these methods to compare among ENDS (e.g. JUUL) users the effect of 5% nicotine concentration, 3% (partial NR) or 0% (total or nicotine-free) NR on dependence, satisfaction, puffing behavior, clinical outcomes, and toxicant exposure. Our overarching hypothesis is that NR for ENDS will be associated with less satisfaction, withdrawal suppression, and intention to use and that such an effect will be more pronounced in total vs. partial NR. Our secondary hypothesis is that with very low nicotine ENDS and low dependence users, NR will cause minimal compensatory puffing and increased exposures. We will recruit current ENDS users (n=120; 21-35 yrs), for a 2X2 within- subject factorial crossover lab study. The nicotine conditions (5%, 3%) or (0%, 5%) x 2 time (pre-post) are the within-subject factors. A follow-up call at 3-months post-lab will be made to assess nicotine preference and changes in ENDS use.

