Experimental protocol. Participants from each frequency group will be randomly assigned to one of the nicotine concentration conditions and attend the lab for two, ~2-h sessions, separated by a 48-h washout period, and differ by nicotine concentration (3%,5%) or (0%, 5%). Session order will be counterbalanced to mitigate order and carry-over effects. At the beginning of the 1st session, participants will provide consent, complete demographic and personal information including age, sex, socioeconomic status, race/ethnicity, and detailed tobacco/nicotine use history. Participants will get familiarized with the study procedures, measures, and they will be given time to adapt to the lab. After adaptation, continuous measurement of physiological responses begins, and 10 ml of venous blood is sampled, lung function tests will be conducted, and participants are asked to respond to subjective measures (pls. see below Outcome Measures). Participants will inhale on their session ENDS ad libitum for up to 60 minutes (as in Vargas-Rivera et al., 2020). At the end of the ENDS use period 10 ml of blood will be sampled, lung function tests repeated, and subjective measures assessed. The session will terminate 30 minutes after the last puff, and the 2nd session is scheduled. A follow-up phone call at 3-month post-study will be made to evaluate nicotine preferences and changes in ENDS and tobacco use.

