## **AIM 1: To assess the subjective and clinical effects of nicotine reduction on ENDS users.**

Objective and hypothesis. This aim will help understand users' response to NR and how it will influence their product satisfaction, nicotine dependence, intention to quit or use in the future, lung functions, and clinical symptoms. We hypothesize that NR will be associated with less satisfaction, withdrawal suppression, and intention to use in the future and that such an effect will be more pronounced in total compared to partial NR and in high compared to low-frequency users.

Outcomes. We will utilize our clinical lab model to study the effect of NR on the following outcomes assessed according to the plan described in Table 2. All assessments will be based on instruments that are standard in clinical lab studies of addictive behaviors modified for the ENDS we plan to use (Vargas-Rivera et al., 2020). Participants will use a tablet to respond to these measures using RedCap.

**Outcomes.** We will utilize our clinical lab model to study the effect of NR on the following outcomes assessed according to the plan described in Table 2. All assessments will be based on instruments that are standard in clinical lab studies of addictive behaviors modified for the ENDS we plan to use (Vargas-Rivera et al., 2020). Participants will use a tablet to respond to these measures using RedCap. Briefly, we will assess;

1. Demographic and baseline characteristics; including age, race, sex, and reasons for ENDS use. Other characteristics will include the frequency of ENDS use, and the history of other tobacco/nicotine products use (Amato, Boyle & Levy, 2016; Zavala-Arciniega et al., 2019; Vargas-Rivera et al., 2020).
2. Dependence measures including; 1) *Use satisfaction* (Modified Cigarette Evaluation Questionnaire (mCEQ) (Arger et al., 2017); 2) *Dependence* (Questionnaire of Smoking Urges-brief and the Minnesota Nicotine Withdrawal Scale, Penn State Electronic Cigarette Dependence Index (Ben Taleb et al., 2018; Foulds et al., 2015; St Helen et al., 2017); 3) *Puff sensory effects* (Duke Sensory Scale, (Malson & Pickworth, 2002)).

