## **AIM 3: To assess exposure to toxicants associated with nicotine reduction.**

**Objective and hypothesis:** This aim will help elucidate how compensatory puffing behavior in response to NR affects exposure to pulmonary toxicants. *We hypothesize that partial but not total NR will be associated with compensatory puffing behavior that will, in turn, lead to greater exposure to toxicants.*

**Analytical methods.** The analytical assessments will be conducted at the AUB Aerosol Research Laboratory (ARL). The ARL is equipped with two digital playback smoking machines necessary for Aim 3. These two machines, developed and tested by our team at AUB, are to our knowledge unique to this setting and are not available in any other laboratory. The proposed work in Aim 3 is built on the ARL framework and infrastructure for aerosol generation, sampling, and chemical analysis.

**Aerosol generation and sampling:** The deidentified puff topography data will be shared via Microsoft Sharepoint between FIU and AUB Aerosol Lab, thus, all communication will be encrypted between client and server using SSL 2048 bit keys. Access to the lab and data will be granted only by permission of Drs. [name] (PI), and [name] (local PI at AUB).

Once the puff topography files have been received by the ARL, we will use ALVIN (Aerosol Lab Vaping Instrument) (Talih et al., 2015, 2017) to draw aerosols from the ENDS devices, for each of the 240 topography sessions. For each session, ALVIN will be programmed to reproduce the puff topography data generated in the clinical lab. The generated aerosol will be drawn through a Gelman type A/E 47mm glass fiber filter followed by a 2,4-dinitrophenylhydrazine-coated silica cartridge (type LpDNPH H10) cartridge, for nicotine and aldehydes quantification, respectively (see Talih et al., 2015, 2017; El-Hellani et al., 2018 for more detail). The pods (e.g. JUUL) and batteries will be shipped from the same batch as those used at FIU to minimize biases. A new pod will be used for every session. Each pod will be pre-conditioned before sampling by drawing 15 4-second puffs at 1 LPM using ALVIN. We will use a quality assurance protocol and ENDS electrical performance tester developed at the ARL to ensure that each battery and pod are within tolerance (Talih et al., 2019, 2020b).

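### Partial reduction is tested only on NJOY and total reduction only on SREC, so a difference between the two effects cannot be attributed to the size of the nicotine reduction

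*Combined protocol and SAP*

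**What the plan says.** - **Devices.** Under Study Design, "the first part will be 2X2 comparing NJOY 5% and 3% to test the effects of partial nicotine reduction", while "the second part will be using the NIDA Standardized Research Electronic Cigarette (SREC) for Clinical Research 5% and 0% (placebo"). The purpose of part 2 is "to test the effect of the total reduction using the same pods and juices from the same manufacturer". This reads as constancy between the two sessions of that part. Nothing says that NJOY and SREC are matched.
- **Questions.** The Background says that judging nicotine reduction (NR) "requires standardized comparisons involving a range of NR levels", and it lists partial versus total NR, for compensatory puffing and exposure, among three main regulatory questions. Aim 1 expects that "such an effect will be more pronounced in total compared to partial NR and in high compared to low-frequency users". Aim 3 expects that "partial but not total NR will be associated with compensatory puffing behavior".
- **Allocation.** The Experimental protocol paragraph says: "Participants from each frequency group will be randomly assigned to one of the nicotine concentration conditions". Session order is counterbalanced.
- **Analysis.** The primary model in Statistical analysis has two within-subject factors, the concentration pair and time. Aim 3 uses a one-way ANOVA of NR on aldehyde emissions. There is no part or device term, no specified partial-versus-total contrast, no comparison of the two 5% sessions and no caveat about device. The between-subject factor in the power calculation is use frequency.

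**The concern.** The protocol wants to say whether removing nicotine altogether acts differently from lowering it. Each degree of reduction has its own device, so a different response in the two parts has two possible sources: the size of the reduction, or a device on which any reduction acts differently. No model term can separate them, because the cells that would do so are not studied.

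At stake are the regulatory question on partial versus total NR and the comparative parts of the overarching, Aim 1 and Aim 3 hypotheses. The Participants section relies on one product type and brand so that outcomes reflect the session's condition. That holds within a part but not between parts.

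**Working it through.** **1. Cells studied**

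| | 5% | 3% | 0% |
|---|---|---|---|
| NJOY (part 1) | yes | yes | no |
| SREC (part 2) | yes | no | yes |

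**2. What each comparison estimates.** Write the mean on device d at concentration c as a(d) + g(c) + h(d,c): device effect, concentration effect and interaction. N is NJOY and S is SREC.

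- Partial effect, NJOY 5% minus 3%: g(5) − g(3) + h(N,5) − h(N,3). The device effect a(N) has gone.
- Total effect, SREC 5% minus 0%: g(5) − g(0) + h(S,5) − h(S,0). The device effect a(S) has gone.
- Total minus partial: g(3) − g(0) + [h(S,5) − h(S,0)] − [h(N,5) − h(N,3)]. Additive device effects cancel. The bracketed interaction terms remain and cannot be estimated from these four cells.
- Direct 3% v 0%: g(3) − g(0) + [a(N) − a(S)] + h(N,3) − h(S,0). The device main effect is now included.

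**3. Aim 3 one-way ANOVA, if pooled over both devices.** Assume equal parts, so that the 240 playback sessions are 60 in each of the four cells, and set h to zero. The pooled 5% mean carries [a(N) + a(S)]/2, the 3% mean carries a(N) and the 0% mean carries a(S). Then:

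- 5% v 3% is off by [a(S) − a(N)]/2;
- 5% v 0% is off by [a(N) − a(S)]/2;
- 3% v 0% is off by a(N) − a(S).

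Pooling would thus bring a device effect even into contrasts that are clean within a part.

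**4. The plan's own figures.**

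- Dropout: 120/(1 − 0.20) = 150, as stated.
- Within-subject power, with N = 120, four repeated measures, correlation 0.5, f = 0.1 and a one-degree-of-freedom test: noncentrality = 0.1² × 120 × 4/(1 − 0.5) = 9.6, power 86.7%.
- Between-subject power at f = 0.2: noncentrality = 0.2² × 120 × 4/(1 + 3 × 0.5) = 7.68, power 78.5%, close to the stated 80%.

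These figures pool both parts and do not address a partial-versus-total contrast.

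**5. Scale of the problem.** Assume 60 per part (the 2X60 in the Sample size paragraph could instead mean frequency groups). Work in SDs of the within-person difference, 5% minus reduced.

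- Standard error of total minus partial: √(2/60) = 0.183.
- Effect detectable with 80% power: (1.960 + 0.842) × 0.183 = 0.51 SD. Power is 19% at 0.2 SD and 59% at 0.4 SD.
- If the true partial and total effects are equal, the chance of a significant contrast for an interaction δ is 1 − Φ(1.96 − δ/0.183) + Φ(−1.96 − δ/0.183):

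| δ (assumed) | Significant contrast |
|---|---|
| 0 | 5.0% |
| 0.1 | 8.5% |
| 0.2 | 19.5% |
| 0.3 | 37.6% |
| 0.5 | 78.2% |

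The documents give no value for δ. The table only shows sensitivity.

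**The case against.** The strongest reply is that each part carries its own 5% session on the same device and each participant is their own control. That is correct and limits the point: both within-part effects are free of device confounding, and additive device differences drop out when they are compared. Only the attribution of a difference between them is at risk.

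Four stronger readings are tempting, and the documents do not support them.

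- *Calendar time is a second confound.* A reader might infer this from the labels first and second part. They may be plain enumeration. No section says the parts run in sequence, and random assignment to a concentration pair implies that both are open together. The two statements need reconciling, but that is an ambiguity and not a demonstrated bias.
- *The Aim 3 finding could be nothing but a device difference.* It can be read as two within-device questions, 5% v 3% on NJOY and 5% v 0% on SREC. Neither answer, analysed within its part, can come from a difference between the devices.
- *The confound can be sized from an assumed ratio of nicotine delivery.* The result depends on the scale. In absolute units it changes with the ratio. In proportional terms, if delivery follows the label, SREC is a 100% reduction and NJOY a (5 − 3)/5 = 40% reduction whatever the ratio. Use is also ad libitum.
- *Similar 5% sessions would clear the comparison.* They would not exclude an interaction at the reduced level. With 60 per part, the 95% interval for the 5% difference has a half-width of 1.96 × 0.183 = 0.36 SD of the outcome, so a non-significant result would not show equivalence. Nor would a difference at 5% prove an interaction.

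**Conclusion.** The point holds as a limit on one conclusion. The aliasing of device with degree of reduction is complete and follows from Study Design alone, without any numerical assumption. The NJOY 5% v 3% effect and the SREC 5% v 0% effect can each be estimated and interpreted on their own. The claim that total reduction acts more strongly than partial reduction, or that compensation differs between them because of the size of the reduction, cannot be supported by this design.

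How far a comparison would mislead depends on a device-by-reduction interaction that the documents do not quantify. The error rates above rest on assumed interactions and an assumed 60 per part. On the same assumption the contrast detects only about 0.51 SD with 80% power, which also argues for calling it exploratory. For Aim 3, the device main effect enters only if the one-way ANOVA is pooled over devices, which the text does not settle.

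**What to change.** 1. Analyse each reduction within its own device. For aldehydes in Aim 3, replace any one-way ANOVA pooled over devices with a paired comparison of 5% and the reduced concentration within each part.
2. Make any partial-versus-total comparison a part-by-reduction contrast of the within-person differences. Label it in every case as an exploratory cross-device comparison (NJOY 5% to 3% v SREC 5% to 0%), and do not attribute it to the size of the reduction alone. Align the Background, Aim 1 and Aim 3 with this.
3. Report NJOY 5% against SREC 5% on topography, plasma nicotine boost, and playback nicotine and aldehydes, with confidence intervals. Report each reduction also as the drop in delivered nicotine. Treat both as descriptive context, not as a pass/fail test of comparability.
4. Reconcile Study Design with the Experimental protocol paragraph: state that both parts enrol concurrently with randomisation to part or, if they do not, that the between-part comparison is non-randomised.

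The cost is protocol wording and extra analyses of data already planned, with no new sessions. If enrolment is to be concurrent, both products must be in stock together. The downside is a weaker partial-versus-total conclusion. Randomisation to part would balance the participants but would not remove the aliasing with device.

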## **Participants and recruitment**

Participants: We will recruit 120 current ENDS users defined as using ENDS either daily or occasionally in the past 30 days (as in Vargas-Rivera et al., 2020). Individuals who report smoking cigarettes or other tobacco/nicotine products will be included to increase the generalizability of results and enhance recruitment provided that they don't use these tobacco products >5 times/past month (as in Ben Taleb et al., 2020). As our study focuses on nicotine dependence related parameters, any substantial use of other tobacco/nicotine products will likely bias our planned assessments. Similarly, the pre-study 12 hours abstinence period from all tobacco/nicotine products and using the same product type/brand ensures that study outcomes reflect mainly each session's condition. We aim to recruit equal numbers of men and women.

Inclusion and exclusion criteria: Participants need to be generally healthy, between 21-35 years old, provide written informed consent, and agree to attend the lab on two occasions and use their ENDS product according to the study protocol. Participants will be asked to abstain from

ENDS and all tobacco/nicotine products use for at least 12 hours prior to each session. The abstinence period is needed to clear nicotine from prior-to-study use and ensure that all study measures are influenced mostly by the study conditions. Testing short-term abstinence of ENDS, which does not produce carbon monoxide (CO) is an ongoing challenge (Hiler et al., 2017). Therefore, we will follow published recommendations (Blank et al., 2016) to use the gold standard of plasma nicotine to eliminate data from non-compliant participants later. Because this will entail a loss of data, we will try to minimize that and improve compliance by asking the participants to arrive at the scheduled study sessions one hour early for an observation period, and complete a CO test (Blank et al., 2016). The CO test will be good to detect combustible tobacco products' use (e.g. cigarette smoking), and act as a bogus pipeline for ENDS use (Blank et al., 2016). This procedure has been shown to cut participants' non-adherence to the abstinence condition to <10% (Spindle et al., 2018), which is consistent with our own experience (Vargas-Rivera et al., 2020). A blood draw will be completed before each session, abstinence will be confirmed using plasma nicotine levels less than 5 ng/ml (Benowitz, Hukkanen, & Jacob, 2009).

Individuals with a self-reported history of chronic disease, psychiatric conditions, history of cardiovascular disease, low or high blood pressure (BP) (systolic BP>150 mm Hg, or diastolic BP>100 mm Hg), seizures, or regular use of prescription medications (other than vitamins or birth control) will be excluded (St Helen et al., 2017). This will be assessed by history and physical examination conducted by the research nurse during a screening visit. The research nurse will have access to an on-call Medical Monitor (physician) in case of concern or for consultation at any point during the study (as is the current practice in our lab). The physical examination will include measuring BP, heart rate (HR), temperature, pulse oximetry, and weight/height. Importantly, considering the current COVID-19 pandemic we will follow CDC and FDA guidelines for clinical research and COVID-19 to minimize any potential risk of infection transmission as detailed in our Human Subject Protection part (CDC, 2020b; FDA, 2020c).

Briefly, we will apply a protocol consisting of 5 main areas;

- 1- Screening of Participants for COVID-19;
- 2- Social and Physical Distancing;
- 3- Use of Personal Protective Equipment (PPE);
- 4- Cleaning and disinfecting;
- 5- Personal Hygiene and Hand Washing.

Participants with symptoms/history suggestive of COVID-19 (e.g.  $\geq 100.4^{\circ}\text{F}$ , cough, contact) or with a history of cannabis use (risk for e-cigarette or vaping product use-associated lung injury-EVALI) will be excluded from participation (details in Human Subjects Protection). As knowledge about COVID-19 is rapidly evolving we will apply best practices at the time of study to protect human

subjects and our staff (e.g. require vaccination record if such becomes feasible). FIU has started providing vaccination to all research staff with direct contact with human subjects, and free-of-charge COVID-19 testing facilities have become available within and in the vicinity of FIU (e.g. FIU-Curative., 2020). Women will be excluded if they are breast-feeding or test positive for pregnancy (by urine pregnancy testing) at screening (St Helen et al., 2017). Finally, we will also exclude individuals if they intend to quit e-cigarette within the next 3 month and if they use THC in e-cigarette.

Recruitment: We will recruit participants using a combination of online, offline, and in-person recruitment methods to ensure successful recruitment (Buller et al., 2012). Offline items such as posters, flyers, and study inserts will be posted and distributed on FIU and other university campuses in Miami (e.g. University of Miami), nearby off-campus locations, and around ENDS shops in Miami. Online recruitment will include student listservs, Facebook, and other social media. In-person recruitment will involve handing out flyers and word-of-mouth targeting vape shops in Miami. Recruitment materials will be Institutional Review Board (IRB) approved and will have contact information (phone, e-mail) for initial eligibility screening. Based on previous experience, we expect to study 10 subjects/month (Vargas-Rivera et al., 2020). We will continue recruitment until we reach the target sample (120 with complete sessions). While recruitment is

always a challenge, [name]'s lab has easily recruited JUUL users in the past year with negligible drop out for 2 session protocol using comparable incentives, to the extent that we had to turn down many eligible participants due to sampling saturation (Vargas- Rivera et al., 2020). This is due to the widespread use of ENDS, and JUUL among young adults, especially in a large university with about 57,000 students such as FIU, where our lab is located. Participants completing the on-site screening and 2 lab sessions, and 3-month phone follow-up will be compensated a total \$200 at the end of the study to encourage completeness.

Screening, and informed consent: Individuals who are identified as potentially eligible based on the phone screening will be asked to attend an onsite-screening, which will involve assessment of inclusion/exclusion criteria, physical examination, COVID-19 screening, and urine pregnancy testing for women. Prior to screening, potential participants will undergo a review of the study and consent procedures to ensure that they understand the study, its risks/benefits, and their rights as research participants. Consented (written) individuals will then undergo a physical examination conducted by the research nurse, who will have access to an on-call Medical Monitor (physician) in case of concern or for consultation at any point of the study as it is the standard practice in our lab. Successfully consented participants will be scheduled for their 1st session and asked to abstain from all tobacco/nicotine use 12 hours prior to it.

Sample size. All power calculations were performed with PASS19 (PASS, 2019). We built our calculation of the sample size for this study based on our preliminary study of the effect of NR on subjective (e.g. craving, urges) and puff topography measures (pls. see Preliminary Studies), where medium effect size (Cohen's  $f=0.2$ ) depending on nicotine condition was detected. Expecting a maximum 20% loss due to noncompliance with abstinence or study protocol (Vargas-Rivera et al., 2020), this study will include a dropout inflated sample of 150 ENDS users. Using repeated measures ANOVA F-test with 2 within and 1 between factors, a total dropout adjusted sample size of 120 (2X60) participants will have at least 80% power to detect small to medium-size effect (Cohen's  $f=0.1-0.2$ ) or larger for 2 within-subject (NR condition and time) and 1 between subject (use frequency) factors, as well as their interactions at 0.05 level of significance, assuming sphericity and a moderate correlation (0.5) among repeated measures (Cohen, 1988).

Experimental protocol. Participants from each frequency group will be randomly assigned to one of the nicotine concentration conditions and attend the lab for two, ~2-h sessions, separated by a 48-h washout period, and differ by nicotine concentration (3%,5%) or (0%, 5%). Session order will be counterbalanced to mitigate order and carry-over effects. At the beginning of the 1st session, participants will provide consent, complete demographic and personal information including age, sex, socioeconomic status, race/ethnicity, and detailed tobacco/nicotine use history. Participants will get familiarized with the study procedures, measures, and they will be given time to adapt to the lab. After adaptation, continuous measurement of physiological responses begins, and 10 ml of venous blood is sampled, lung function tests will be conducted, and participants are asked to respond to subjective measures (pls. see below Outcome Measures). Participants will inhale on their session ENDS ad libitum for up to 60 minutes (as in Vargas-Rivera et al., 2020). At the end of the ENDS use period 10 ml of blood will be sampled, lung function tests repeated, and subjective measures assessed. The session will terminate 30 minutes after the last puff, and the 2nd session is scheduled. A follow-up phone call at 3-month post-study will be made to evaluate nicotine preferences and changes in ENDS and tobacco use.

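### Recruitment is given as 120 in some places and 150 in another, and the stopping count does not require verified abstinence, so the 120 analysable participants behind the power statement may not be delivered

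*Combined protocol and SAP*

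**What the plan says.** Five places bear on the sample size.

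- **Background:** "We will recruit current ENDS users (n=120; 21-35 yrs".
- **Participants and recruitment, Participants:** "We will recruit 120 current ENDS users".
- **Same section, Recruitment:** "We will continue recruitment until we reach the target sample (120 with complete sessions").
- **Same section, Sample size:** "Expecting a maximum 20% loss due to noncompliance with abstinence or study protocol", the plan states that "this study will include a dropout inflated sample of 150 ENDS users". The power statement then rests on "a total dropout adjusted sample size of 120 (2X60) participants". It claims at least 80% power for Cohen's f of 0.1 to 0.2, at a 0.05 significance level and a correlation of 0.5.
- **AIM 3, Aerosol generation and sampling:** machine playback is planned "for each of the 240 topography sessions", which is 120 × 2.

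On abstinence, the inclusion criteria say the study will "use the gold standard of plasma nicotine to eliminate data from non-compliant participants later", with a limit of 5 ng/ml, and accept that data will be lost this way. They cite non-adherence below 10% under the observation and CO procedure. The plasma nicotine paragraph under AIM 2 has samples frozen for later analysis.

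**The concern.** In the Sample size paragraph, 120 is what is left after losses. In Background and Participants, 120 is what is recruited. The Recruitment paragraph could settle the matter, but it counts people with complete sessions. Someone who vaped during the abstinence period can attend both sessions, finish every measurement and be counted, then be removed once plasma is assayed. The CO test on the day does not close this gap: the plan notes that ENDS produce no CO and that, for ENDS use, the test works only as a bogus pipeline.

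Abstinence failure is one of the two losses that the 20% allowance is meant to cover, yet the stopping count is not said to take account of it. If the count is followed as plainly read, the analysed sample is smaller than the one behind the power statement. Staff who read different paragraphs could also work to different enrolment targets.

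**Working it through.** **Inputs.** From Sample size: 120 analysable, 150 included, maximum loss 20%, f = 0.1 to 0.2, alpha 0.05, correlation ρ = 0.5, two within-subject factors (so four measurements per person) and one between-subject factor. From the inclusion criteria: abstinence non-adherence below 10%. Assumptions of this check: two use-frequency groups, and the 10% read as a proportion of participants.

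**The plan's inflation.** 120 / (1 − 0.20) = 150, and 150 × 0.80 = 120. The Sample size paragraph is arithmetically correct.

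**The plan's power at N = 120.** Noncentral F with 1 and N − 2 degrees of freedom, all participants pooled.

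- Within-subject effect: λ = f² × 4N / (1 − ρ). At f = 0.1, λ = 0.01 × 480 / 0.5 = 9.6 and power is 0.867.
- Between-subject effect: λ = f² × 4N / (1 + 3ρ). At f = 0.2, λ = 0.04 × 480 / 2.5 = 7.68 and power is 0.785.

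These agree with the stated 80% for f of 0.1 to 0.2, to within 2 points for the between-subject factor. The claim therefore depends on 120 analysable people in total.

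**Analysable number if recruitment stops at 120 completers and non-abstinent data are then removed.**

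- 10% removed: 120 × 0.90 = 108.
- 20% removed: 120 × 0.80 = 96.

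| Analysed | λ within, f = 0.1 | Power | λ between, f = 0.2 | Power |
|---|---|---|---|---|
| 120 | 9.60 | 0.867 | 7.68 | 0.785 |
| 108 | 8.64 | 0.830 | 6.91 | 0.741 |
| 96 | 7.68 | 0.783 | 6.14 | 0.689 |

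Within-subject power at f = 0.1 reaches 0.80 at about N = 100, a loss after completion of about 20 / 120 = 17%. At f = 0.2, within-subject power is above 0.99 in all three rows.

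**Completers needed to keep 120.** At 10% removal, 120 / 0.90 = 133.3, so 134. At 20% removal, 150.

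**The case against.** A reader might infer that the plan as written fails to deliver 120. The documents do not support that flat statement. If the Sample size paragraph governs, 150 are included, its allowance expressly covers abstinence failures, and 120 remain at the maximum loss. If *complete* means abstinence-verified, the stopping rule itself delivers 120. Both readings are possible, and the target in the Recruitment paragraph may simply be the post-loss 120. What stands is that the text states neither.

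A reader might also take 96 as the expected number. It is a ceiling on the loss. The 20% combines abstinence failure with other protocol noncompliance, and a rule that continues until 120 have complete sessions already replaces people who do not finish. The loss still to come is mainly abstinence failure, for which the plan's own figure leaves about 108. At 108, within-subject power at f = 0.1 is still above 0.80. The preliminary study pointed to f = 0.2, where within-subject power barely moves.

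Nor do the documents show that a shortfall would surface only after recruitment closes. They say later and give no date, so assays during recruitment are not excluded. The 240 playback sessions decide nothing, because they fit 120 analysable people as well as 120 enrolled.

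These objections limit the size of the problem but do not remove the conflict. The between-subject comparison has no slack: it is at 0.785 with all 120, and use frequency carries hypotheses in Aims 1 and 2. The multiple imputation in Statistical analysis is described for rare missing data such as instrument malfunction and is not said to cover abstinence exclusions.

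**Conclusion.** The inconsistency is real and should be corrected; its consequence is conditional and modest. The 120 behind the power statement may not be delivered if recruitment stops at 120 completers whose abstinence has not been verified. On the plan's own abstinence figure the cost is about 4 points of power: 0.87 to 0.83 within subjects at f = 0.1, and 0.785 to 0.74 between subjects at f = 0.2. In the worst case it is about 8 and 10 points, to 0.78 and 0.69. These figures assume pooled analysis of all participants, two frequency groups, the plan's correlation of 0.5, and removal of every participant who fails the plasma check. The fault lies in the definition of the target, not in the inflation arithmetic.

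**What to change.** - Use one enrolment figure throughout: up to 150, as in the Sample size paragraph. Amend Background and Participants to match, and keep 120 for the analysable number.
- In the Recruitment paragraph, define the stopping count as 120 participants (60 per part, taking 2X60 to mean the two parts) with two complete sessions and pre-use plasma nicotine below the plan's own 5 ng/ml limit in both.
- Run the pre-use assays in batches during recruitment so that the count is known while replacement is still possible.
- State that if 150 are enrolled before 120 are verified, the power will be reported for the number reached. A cap of 150 secures 120 only while total loss is at most 20%.
- If the stopping count is left unverified, restate the power for about 108 analysed, with 96 as the worst case.

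The cost is wording and earlier batching of assays already planned. Enrolment stays within the 150 already stated.
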